7.3 Prior, Concomitant and Post-Treatment Medications

A prior medication is defined as any medication taken prior to the date of the first dose of study drug (GLE/PIB). A concomitant medication is defined either as (1) any medication that started prior to the date of the first dose of study drug and continued to be taken on or after the first dose of study drug or (2) any medication that started on or after the date of the first dose of study drug, but not after the date of the last dose of study drug. A post-treatment medication for the treatment of HCV is defined as any medication taken on or after the last dose of study drug and entered as "Post-treatment HCV medications" on the eCRF.

The number and percentage of subjects taking prior medications, concomitant medications, and post-treatment HCV medications will be summarized by generic drug name based on the WHO Drug Dictionary.

8.0 Subject Disposition

The number and percentage of subjects who screen failed for any reason, and for each screen failure reason, will be summarized for all subjects who screen failed.

8.1 Disposition of Safety Population

The number of subjects in each of the following categories will be summarized by investigator for each treatment arm and overall.

- Enrolled subjects;
- Subjects who took at least one dose of study drug;
- Subjects who completed study drug;
- Subjects who prematurely discontinued study drug;
- Subjects who completed the study;
- Subjects who prematurely discontinued from the study;

The number and percentage of subjects who discontinued study drug will be summarized by reason (all reasons) and by primary reason (per eCRF) for each treatment arm and overall. Similar summaries will be provided for discontinuations from the study.

The number and percentage of subjects with reported study drug interruptions will be summarized by treatment arm. Reasons for study drug interruptions will be presented in the CSR listings.

9.0 Study Drug Exposure and Compliance

Exposure and compliance will be summarized on the ITT population by treatment arm and overall.

9.1 Exposure

The duration of exposure to study drug will be summarized for each treatment arm and overall in the safety population. Duration of exposure is defined for each subject as the last study drug dose date minus the first study drug dose date plus 1 day.

During each treatment period, descriptive statistics (mean, standard deviation, median, minimum, and maximum) will be presented for exposure. Study drug duration will also be summarized with frequencies and percentages using the following categories:

- 1 to 15 days
- 16 to 30 days
- 31 to 45 days
- 46 to 60 days
- 61 to 75 days
- 76 to 90 days
- > 90 days

In addition, the number and percentage of subjects with study drug duration of ≥ 52 days for Arm A and ≥ 77 days for Arm B will be summarized.

9.2 Compliance

For each kit, the total number of tablets dispensed and returned is recorded. The compliance for study drug (glecaprevir/pibrentasvir) during the Treatment Period will be calculated as the percentage of tablets taken relative to the total tablets expected to be taken. The total number of tablets expected to be taken will be equal to the total number of tablets that should have been taken per the protocol for the duration that the subject was in the Treatment Period (date of last dose of study drug – date of first dose of study drug + 1). Study drug interruptions recorded on the eCRF will not be subtracted from the duration.

Compliance will be calculated for each subject and summarized with the mean, median, standard deviation, minimum, and maximum by treatment arm. A listing of compliance for each subject will be provided. A subject is considered to be compliant if the percentage is between 80% and 120%. The percentage of compliant subjects will be summarized for each treatment arm based on data as observed.

10.0 Efficacy Analysis

10.1 General Considerations

General Considerations

All efficacy analyses will be performed on the ITT population, unless otherwise specified.

Sensitivity analyses will be conducted for it using the mITT-VF populations.

Missing data will be imputed as described in Section 6.3 for analyses of the HCV RNA endpoints of SVR and for analyses of PROs as described in Section 6.3 and Section 10.9.

Plasma HCV RNA levels will be determined for each sample collected by the central laboratory using the Roche COBAS® AmpliPrep/COBAS® TaqMan® HCV Quantitative Test, v2.0. The lower limit of detection (LLOD) and lower limit of quantification (LLOQ) for this assay (regardless of genotype) are both 15 IU/mL.

HCV RNA results that are detectable but not quantifiable are reported as "< 15 IU/ML HCV RNA DETECTED" and those that are undetectable are reported as "HCV RNA NOT DETECTED" in the database.

The notation "HCV RNA < LLOQ" is used to represent all HCV RNA values < 15 IU/mL, including values reported as "HCV RNA NOT DETECTED" or "< 15 IU/ML HCV RNA DETECTED." HCV RNA \geq LLOQ are all quantifiable values of 15 IU/mL or greater.

Definitions for Efficacy Endpoints

A confirmed quantifiable value during treatment is defined as any two consecutive HCV RNA measurements \geq LLOQ (or 100 IU/mL for **Breakthrough**), either both during treatment or at the final treatment measurement and the next consecutive post-treatment measurement. A confirmed quantifiable post-treatment value is defined as any two consecutive post-treatment HCV RNA measurements \geq LLOQ.

Breakthrough = confirmed HCV RNA \geq 100 IU/mL after HCV RNA < LLOQ during the Treatment Period; or confirmed increase from nadir in HCV RNA (two consecutive HCV RNA measurements > 1 log₁₀ IU/mL above nadir) at any time point during the Treatment Period. A single breakthrough value (\geq 100 IU/mL or > 1 log₁₀ above nadir) followed by lost to follow-up also will be considered a breakthrough (i.e., will not require confirmation).

EOT failure = HCV RNA \geq LLOQ at end of treatment with at least 6 weeks of treatment, where the HCV RNA value must be collected on or after Study Drug Day 36 and study drug duration \geq 36 days.

On-treatment virologic failure = **Breakthrough** or **EOT failure**; if a subject meets both definitions of Breakthrough and EOT failure, he or she will be categorized as Breakthrough only.

SVR₄ = HCV RNA < LLOQ in the SVR₄ window (4 weeks after the last actual dose of active study drug) without any confirmed quantifiable (\geq LLOQ) post-treatment value before or during that SVR window.

SVR₁₂ = HCV RNA < LLOQ in the SVR₁₂ window (12 weeks after the last actual dose of active study drug) without any confirmed quantifiable (\geq LLOQ) post-treatment value before or during that SVR window.

Relapse₁₂ = confirmed HCV RNA \geq LLOQ between end of treatment and 12 weeks after last actual dose of active study drug (up to and including the SVR₁₂ window) for a subject with HCV RNA < LLOQ at Final Treatment Visit who completed treatment (as defined below), excluding HCV reinfection as described below.

Relapse_{overall} = confirmed HCV RNA \geq LLOQ between end of treatment and up to and including the last HCV RNA measurement collected in the Post-Treatment Period for a subject with HCV RNA < LLOQ at Final Treatment Visit who completed treatment (as defined below), excluding HCV reinfection.

Virologic failure rate for SVR₁₂ = any subject who experiences **On-treatment virologic failure** or **Relapse₁₂** out of all ITT subjects.

Only subjects who have at least one post-treatment HCV RNA value will be included in analyses of relapse.

Completion of treatment: For the analysis of relapse, completion of treatment is defined as study drug duration of 52 days or greater for Arm A and 77 days or greater for Arm B. If the last available post-treatment value is \geq LLOQ, then the subject will be considered a relapse (i.e., will not require confirmation).

HCV reinfection: HCV reinfection is defined as confirmed HCV RNA \geq LLOQ after the end of active treatment in a subject who had HCV RNA < LLOQ at Final Treatment Visit, along with the post-treatment detection of a different HCV genotype, subtype, or clade compared with baseline, as determined by phylogenetic analysis of the NS3 or NS5A,

and/or NS5B gene sequences. Reinfection in the case of the same HCV subtype is defined as a clade switch, as indicated by the lack of clustering between the baseline and post-treatment sequences by phylogenetic analysis. If phylogenetic analysis is not possible due to technical difficulties, HCV reinfection may be determined with a confirmed HCV genotype or subgenotype switch by the Versant HCV Genotype Inno-LiPA Assay v2.0 or Sanger assay.

Post-treatment relapse is defined as described earlier (**Relapse₁₂** and **Relapse_{overall}**), and no genotype, subtype, or clade switch compared with baseline as determined by phylogenetic analysis of the NS3 or NS5A gene sequences. If phylogenetic analysis is not possible due to technical difficulties, the subject will be defined as having a post-treatment relapse unless an HCV genotype or subtype switch is confirmed by the Versant HCV Genotype Inno-LiPA Assay v2.0 or Sanger assay.

Reasons for SVR₁₂ Non-Response

Subjects who do not achieve SVR₁₂ (SVR₁₂ non-responders) will be categorized as having:

1. On-treatment virologic failure (see **On-treatment virologic failure** definition);
2. HCV reinfection (see definition described earlier);
3. Relapse₁₂;
4. Prematurely discontinued study drug with no on-treatment virologic failure (defined as any SVR₁₂ non-responder who prematurely discontinued study drug [study drug duration < 52 days for Arm A and < 77 days for Arm B] and did not meet the **On-treatment virologic failure or reinfection** definitions);
5. Missing follow-up data in the SVR₁₂ window (defined as any subject who completed study drug without data in the SVR₁₂ window after applying the imputation rules and not meeting the definitions of [1], [2], [3], or [4]);

6. Other (defined as any SVR₁₂ non-responder not meeting the definitions of [1] – [5]).

For the reasons for SVR₁₂ nonresponse defined above, subjects are only to be counted in 1 category. Specifically, subjects who were SVR₁₂ nonresponders meeting the definition of HCV reinfection will be counted in the reinfection category regardless of whether they meet the definition of prematurely discontinued study drug or relapse₁₂.

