8.1.2.2 Secondary Efficacy Endpoints

The secondary efficacy endpoints are:

- The percentage of subjects with HCV OTVF (defined as confirmed increase of $> 1 \log_{10}$ IU/mL above nadir during treatment, confirmed HCV RNA ≥ 100 IU/mL after HCV RNA < LLOQ during treatment, or HCV RNA \geq LLOQ at the end of treatment with at least 6 weeks of treatment), and
- The percentage of subjects with post-treatment HCV virologic relapse (defined as confirmed HCV RNA \geq LLOQ between end of treatment and 12 weeks after the last dose of study drug among subjects who completed treatment as planned with HCV RNA < LLOQ at the end of treatment; excluding subjects who have been shown to be reinfected)

For the analysis of post-treatment HCV virologic relapse, completion of treatment is defined as any subject with study drug duration of 52 days or greater and 77 days or greater for subjects allocated to treatment durations of 8 weeks and 12 weeks, respectively.

For OTVF and post-treatment relapse, the number and percentage of subjects will be summarized along with a two-sided 95% CI using Wilson's score method.

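### End-of-treatment failure rests on one unconfirmed HCV RNA value and no rule ranks it against SVR12, so an SVR12 responder can also be counted as an on-treatment virologic failure

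*SAP*

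**What the plan says.** OTVF is Breakthrough or EOT failure (SAP 10.1). Breakthrough needs two consecutive results, unless a single one is followed by loss to follow-up. Relapse12 also needs confirmation, unless the last available post-treatment result is quantifiable. EOT failure needs one quantifiable result "at end of treatment with at least 6 weeks of treatment, where the HCV RNA value must be collected on or after" the 36th day of dosing, with at least 36 days of study drug.

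Protocol 8.1.2.2 is built the same way. Its first two OTVF criteria carry the word confirmed. The third, HCV RNA at or above "LLOQ at the end of treatment with at least 6 weeks of treatment), and" so on, does not. SAP 10.4 repeats that wording.

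SAP 10.1 does hold a confirmation rule that would fit: "A confirmed quantifiable value during treatment is defined as any two consecutive HCV RNA measurements" at or above LLOQ (100 IU/mL for Breakthrough), "either both during treatment or at the final treatment measurement and the next consecutive post-treatment measurement". The EOT failure definition does not invoke it.

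SVR12 is HCV RNA below LLOQ "in the SVR₁₂ window (12 weeks after the last actual dose of active study drug) without any confirmed quantifiable" post-treatment value up to that window. For the post-treatment period, "A confirmed quantifiable post-treatment value is defined as any two consecutive post-treatment HCV RNA measurements" at or above LLOQ.

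The virologic failure rate for SVR12 counts OTVF or Relapse12 over all ITT subjects (SAP 10.1), and SAP 10.7 reports virologic failure through Post-Treatment Week 12 with a Wilson interval. The reasons-for-non-response table covers SVR12 non-responders only.

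**The concern.** The SAP treats the same isolated low result differently according to when it falls. A single quantifiable result at Post-Treatment Week 4, followed by one below LLOQ at Week 12, is not a relapse. A single quantifiable result at the end-of-treatment visit is a failure, whatever follows. Breakthrough after suppression needs two results of 100 IU/mL or more; EOT failure needs one at the quantification limit.

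The SVR12 definition cannot see the end-of-treatment result, and OTVF status does not enter it. One subject can thus be a success on the primary endpoint and a failure on a secondary one. At stake is the reading of the OTVF and virologic failure rates, which are expected to be very low, so that one subject is visible. The OTVF count in the secondary analysis could also exceed the OTVF count in the non-response table, with nothing in the SAP to explain the gap.

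**Working it through.** **The plan's own figure.** SAP 4.3 and Protocol 8.2 give a half-width of 3.3% for 97% SVR12 in 100 subjects. 1.96 × √(0.97 × 0.03 / 100) = 3.34%, so it reproduces. The present point does not depend on it.

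**Inputs.**
- LLOQ is 15 IU/mL (SAP 10.1).
- The final treatment value runs to Study Drug End Day 2 (SAP 6.1.2); post-treatment results must fall after that day (SAP 6.2, Table 2).
- HCV RNA is scheduled at end of treatment and at Post-Treatment Weeks 4 and 12 (Protocol Appendices C and D).
- N is about 100, and OTVF has a two-sided 95% Wilson interval (SAP 4.3, 10.4).

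**Step 1: can the end-of-treatment result block SVR12?** No. It lies on or before End Day 2, so it is not a post-treatment value and cannot be one of the two consecutive post-treatment results that block SVR12.

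**Step 2: apply the definitions.** The profiles assume a full 8-week course.

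| End of treatment, PT Week 4, PT Week 12 (IU/mL) | OTVF as written | OTVF if EOT failure is confirmed | SVR12 |
|---|---|---|---|
| 20, <LLOQ, <LLOQ | yes | no | yes |
| 20, 40, <LLOQ | yes | yes | yes |
| 20, 50,000, 1,000,000 | yes | yes | no |
| <LLOQ, <LLOQ, <LLOQ | no | no | yes |

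The first row is the overlap at issue. The second shows that confirmation alone does not remove every overlap: the end-of-treatment and Week 4 results confirm the EOT failure, but only one quantifiable result is post-treatment, so SVR12 stands. A confirmed Breakthrough followed by results below LLOQ after treatment overlaps in the same way.

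**Step 3: size per subject.** The Wilson limits are [p + z²/2n ± z√(p(1−p)/n + z²/4n²)] / (1 + z²/n), with z = 1.96 and n = 100.
- 0/100: 0.0 to 3.7%
- 1/100: 0.2 to 5.4%
- 2/100: 0.6 to 7.0%
- 3/100: 1.0 to 8.5%

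Each overlapping subject adds 1/100 = 1 percentage point.

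**Step 4: effect on the totals.** Suppose 98 of 100 reach SVR12, 2 relapse, and 1 of the 98 has an isolated end-of-treatment result. Then SVR12 is 98%, OTVF 1% and virologic failure (1 + 2)/100 = 3%. SVR12 plus virologic failure comes to 101%.

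**Step 5: how likely is at least one?** The documents give no rate, so any rate is an assumption. With probability r per subject, P(at least one in 100) = 1 − (1 − r)^100. This is 0% for r = 0, 39% for 0.5%, 63% for 1%, 87% for 2%, 95% for 3% and 99% for 5%.

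**The case against.** The strongest reply is that the unconfirmed criterion is deliberate and stable. It stands in Protocol 8.1.2.2 and in SAP 10.1 and 10.4, and the SAP elaborates it with the Day 36 conditions without adding confirmation. Nothing in the documents says that OTVF and SVR12 exclude each other. The one-category rule applies only within the non-response table, which stays internally consistent. The study is open-label, and SAP 12.1 shows that enrolment information was already known (no HIV co-infected subjects), so redefining a protocol endpoint in a way that can only lower the failure rate is unattractive.

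Most of this stands. It means that the SAP does not depart from the protocol here and that the protocol-defined count should not be replaced. It does not remove the double status, for which the SAP has no rule.

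A reader might infer that adding confirmation would keep SVR12 responders out of OTVF. The second row of the table shows that it would not; the absence of a precedence rule is a separate cause. A reader might also take the protocol's pooled data, 23 virologic failures against 2,256 treatment-naïve or TE-PRS subjects (1.0%), as a baseline and say that one such subject doubles the OTVF rate. Those 23 are not split into OTVF and relapse, include one reinfection, and are reported in Protocol 3.0 without a denominator, so they give no OTVF baseline.

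**Conclusion.** The point holds as a gap in endpoint classification. Under the written rules an SVR12 responder can also be an OTVF and a case in the virologic failure rate, and would then be missing from the non-response table. That follows from the definitions and needs no assumption. Whether it will occur is unknown, and zero cases is possible. One case in 100 adds 1 percentage point to both rates, with widely overlapping intervals.

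The documents do not support three stronger readings. The primary result is not biased: the SVR12 count is unchanged, and the subject remains a responder in mITT-VF. The failure rate is not shown to be overstated; it would be so only if such a subject occurs. No subject-management rule is involved, because EOT failure is not among the criteria in Protocol 5.4.1.1. With no hypothesis test planned (SAP 4.3, 10.2), the consequence is limited to how the failure rates read, but the remedy is cheap enough to be worth making.

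**What to change.** Keep the OTVF count of Protocol 8.1.2.2 as the prespecified secondary endpoint. In SAP 10.1 and 10.4:

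- State that subjects who achieve SVR12 are not counted in the virologic failure rate for SVR12. The protocol's list of additional efficacy endpoints (8.1.2.5) does not include this rate, so no protocol endpoint changes.
- Beside the protocol-defined OTVF count, report a second count in which EOT failure must be confirmed by the next consecutive post-treatment result at or above LLOQ. Use the SAP's existing confirmation rule and the Breakthrough waiver for loss to follow-up, and exclude SVR12 responders.
- List every SVR12 responder who meets any OTVF definition.

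Declare these additions in SAP 12.1. The cost is a few sentences, one extra count and one listing. No new samples are needed, because HCV RNA at Post-Treatment Week 4 is already scheduled. The small downside is that two OTVF counts appear, and the added one can only be equal to or lower than the protocol count, so the protocol count should stay the lead figure.

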10.4 Secondary Efficacy Analyses

The secondary efficacy endpoints are:

- The percentage of subjects with HCV on-treatment virologic failure (defined as confirmed increase of > 1 log₁₀ IU/mL above nadir during treatment, confirmed HCV RNA ≥ 100 IU/mL after HCV RNA < LLOQ during

treatment, or HCV RNA \geq LLOQ at the end of treatment with at least 6 weeks of treatment), and

- The percentage of subjects with Relapse₁₂ (defined as confirmed HCV RNA \geq LLOQ between end of treatment and 12 weeks after the last dose of study drug among subjects who completed treatment as planned with HCV RNA $<$ LLOQ at the end of treatment; excluding subjects who have been shown to be reinfected).

For the analysis of post-treatment HCV virologic relapse, completion of treatment is defined as any subject with study drug duration of 52 days or greater and 77 days or greater for subjects allocated to treatment durations of 8 weeks and 12 weeks, respectively.

For on-treatment virologic failure and post-treatment relapse, the number and percentage of subjects will be summarized along with a two-sided 95% CI using Wilson's score method.

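### SAP 10.1 waives confirmation for relapse on a last value but not for reinfection, so a switch proven only on the PT Week 12 sample cannot be classed as reinfection

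*SAP*

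**What the plan says.** SAP 10.1 defines confirmation after treatment: "A confirmed quantifiable post-treatment value is defined as any two consecutive post-treatment HCV RNA measurements" at or above LLOQ (15 IU/mL). Relapse12 and reinfection are both built on it.

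- **Relapse12** applies to a subject below LLOQ at the Final Treatment Visit "who completed treatment (as defined below), excluding HCV reinfection as described below". The paragraph on completion of treatment then relaxes confirmation when the last available post-treatment value is quantifiable: "then the subject will be considered a relapse (i.e., will not require confirmation".
- **Reinfection** has no matching relaxation: "HCV reinfection is defined as confirmed HCV RNA" at or above LLOQ after treatment, together with a different genotype, subtype or clade from baseline.
- **A further paragraph on relapse** adds a separate condition: "and no genotype, subtype, or clade switch compared with baseline as determined by phylogenetic analysis of the NS3 or NS5A gene sequences".
- **SAP 10.4**, like Protocol 8.1.2.2, defines the secondary relapse endpoint "excluding subjects who have been shown to be reinfected".

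In the list of reasons for SVR12 non-response, category 2 only points back to the reinfection definition ("HCV reinfection (see definition described earlier"). Category 4 takes premature discontinuers who "did not meet the On-treatment virologic failure or reinfection definitions". Category 6, Other, takes whoever is left. Reinfection outranks relapse and premature discontinuation, but only for subjects who meet its definition.

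Protocol Appendix D schedules post-treatment HCV RNA at PT Weeks 4 and 12 (or at a PT discontinuation visit), with a resistance sample at the same visits. SAP 10.8 sequences post-treatment samples of 1000 IU/mL or more from SVR12 non-responders.

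**The concern.** A first positive at PT Week 12 is, on the planned schedule, both a single value and the last one. The Protocol's instruction on confirmatory HCV RNA testing (5.4.1.1) concerns failure during study drug treatment, and no post-treatment retest is prescribed. The sample that shows the viraemia can also show by sequencing that the virus is a different one. The subject has then been shown to be reinfected, yet fails the SAP's reinfection definition for want of a second HCV RNA value. The precedence rule, which exists to keep reinfections out of relapse, never comes into play.

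The definitions also disagree on where the subject goes instead. The waiver sentence points to relapse; the no-switch condition and SAP 10.4 point away from it. The stakes are the table of reasons for non-response and, if the waiver is programmed literally, a secondary endpoint, the virologic failure rate and membership of mITT-VF.

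**Working it through.** **The plan's own figure.** SAP 4.3 gives a 95% half-width of 3.3% at 97% SVR12 and N = 100. Check: 1.96 × √(0.97 × 0.03 / 100) = 0.0334, so it reproduces. The point does not depend on it.

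**Tracing one subject.** Final Treatment Visit below LLOQ; PT Week 4 below LLOQ; PT Week 12 at 1000 IU/mL or more, with a clade switch on sequencing; no later sample.

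| Rule (SAP 10.1 unless stated) | Completer | Premature discontinuer |
|---|---|---|
| SVR12 (last value in window below LLOQ) | No | No |
| 1. On-treatment virologic failure | No | No |
| 2. Reinfection (two consecutive values) | No, only one value | No, only one value |
| 3. Relapse12, waiver sentence read alone | Yes | No, did not complete |
| 3. Relapse12, with the no-switch condition and SAP 10.4 | No | No |
| 4. Premature discontinuation | No | Yes |
| 5. Missing SVR12 data | No | No |
| Resulting category | Relapse12 or Other | Category 4 |

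No column reaches category 2.

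**Size, completer.** Assume N = 100, all complete treatment, this subject is the only non-responder, and Wilson 95% intervals are used.

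| Subject counted as | Relapse12 | mITT-VF SVR12 | ITT SVR12 |
|---|---|---|---|
| Relapse12 | 1/100 = 1.0% (0.18 to 5.45) | 99/100 = 99.0% (94.55 to 99.82) | 99/100 |
| Other | 0/100 = 0% (0 to 3.70) | 99/99 = 100% (96.26 to 100) | 99/100 |
| Reinfection (after the fix) | 0/100 = 0% (0 to 3.70) | 99/99 = 100% (96.26 to 100) | 99/100 |

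The second and third rows agree on every rate; only the label in the non-response table differs. Dropping the subject from the relapse denominator gives 0/99 = 0% (0 to 3.74).

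At the plan's 97% the shift is similar. Assume three non-responders: one true relapse, one non-virologic failure, and this subject. mITT-VF is then 97/98 = 98.98% (94.44 to 99.82) under Other and 97/99 = 97.98% (92.93 to 99.44) under Relapse12.

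**How often.** Protocol Section 3.0 reports one reinfection among 23 virologic failures in treatment-naïve and TE-PRS subjects, a group of 2256 in its Table 2. Assuming that rate carries over, 100/2256 = 0.044 expected reinfections, and the chance of at least one is 1 − (1 − 1/2256)^100 = 4.3%. At five times that rate, 500/2256 = 0.22 expected and a chance of about 20%. The scenario is narrower than any reinfection: first positive at PT Week 12, enough RNA to sequence, and no retest.

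**The case against.** A reader might infer that the plan counts proven reinfections as drug failures, inflating the relapse rate and lowering the mITT-VF result. The documents taken together do not support that. The waiver sentence explains itself as removing the need for confirmation; it does not say that the other elements of relapse lapse. Read with nothing else, it would even make a relapse of a completer who was already quantifiable at the Final Treatment Visit, which Relapse12 rules out. The no-switch condition does not depend on confirmation, and neither does the exclusion in SAP 10.4 and Protocol 8.1.2.2. The better-supported result is Other, which is not virologic failure, so no rate changes. This part of the objection stands and limits the point. It does not remove the textual conflict, because the exclusion inside Relapse12 refers to reinfection as the SAP defines it, which means confirmed.

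It would also be too strong to say that relapse never needs two values. It does, except for a last available value.

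Confirmation is obtainable. Any two consecutive measurements qualify, the SVR12 window runs to Study Drug End Day 126, and the reinfection definition sets no end date, so a positive unscheduled retest would resolve the case. That is true, but nothing in the plan asks for the retest.

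A stricter standard for reinfection than for relapse can be defended, since reinfection takes a subject out of virologic failure in the drug's favour. Protocol Table 2 notes eleven subjects typed as GT2 by the central laboratory whom phylogenetic analysis identified as GT1, so a loose assay rule could turn true relapses into reinfections. This stands as a constraint on the wording of the fix. It does not justify ignoring a switch shown by phylogenetic analysis.

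**Conclusion.** The gap is real and narrow. As written, a subject whose only quantifiable post-treatment value is at PT Week 12, with a switch shown by sequencing and no retest, cannot be recorded as reinfected. A completer goes to Other (better supported) or Relapse12 (literal waiver sentence), and a premature discontinuer goes to category 4.

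The non-response table is wrong in each case. Primary ITT SVR12 is unaffected. Relapse12, the virologic failure rate and mITT-VF move by one subject, about 1 percentage point at N of about 100, only on the literal reading. The sizes assume a single such case; the frequency estimate assumes that the sponsor's earlier program is a fair guide. No efficacy hypothesis is tested, so no decision rule turns on this. It merits correction because the stated rule fails to deliver the exclusion of reinfection that the plan promises, and because the study is open-label, the choice should be settled before anyone has a case in front of them.

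**What to change.** Add two statements to SAP 10.1:

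1. Where a subject's final post-treatment HCV RNA result on record is at or above LLOQ, and phylogenetic analysis of that sample shows a genotype, subtype or clade different from baseline, class the subject as HCV reinfection without a second HCV RNA value. This takes precedence over the last-value rule for relapse.
2. The last-value rule for relapse waives confirmation only. Every other relapse condition, including the absence of a switch, still applies.

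Keep the SAP's existing hierarchy: Inno-LiPA or Sanger results count only when phylogenetic analysis is not possible, and only for a confirmed switch.

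The cost is two sentences and the matching line of derivation code. No visit, sample or protocol amendment is needed, since the PT Week 12 resistance sample and its sequencing at 1000 IU/mL or more are already planned.
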